#### TRAINING (concurrent with recruitment)

- The sponsor shall review the education and experience of personnel proposed as study staff.
- The principal investigator and staff shall be trained by the sponsor regarding the proper use of the device and the details of the study protocol.

#### TREATMENT (total time of activity, 14-18 weeks - 4-6 weeks for the 1st, 2nd, and 3rd treatment applications, and 12-14 weeks following the 3rd treatment for follow-up visit):

##### Individual Treatment Session (approximately 70 minutes)

###### Prior to the Treatment (about 10 minutes):

- The patient is scheduled to arrive at the study site to undergo a treatment.
- The date of the treatment and the time of arrival will be documented in the treatment session record.
- During the first treatment only: The patient is given the Q-Pre Survey to fill out.
- The assigned pre-treatment investigator measures the waist circumference of the patient and documents this in the Pre-Treatment record, with these measurements being made by the blinded assessment clinician as described in the Measurement Tools and Methods section of this protocol.
- Prior to Treatments 2 and 3, the patient will be asked for the study diary, and the pre-treatment investigator shall review the diary and the patient's previous post-treatment Anticipated Effects and Adverse Event forms and discusses with the patient the items that are recorded about any abnormal body functions or observations that may be relevant to the treatment. If any are indicated, these will be documented in the patient record. Additional record shall be made by the investigator as to whether past events and observations have been resolved or are still unresolved.
- The patient is moved to the treatment area.

###### Application of the Treatment (approximately 45 minutes):

- The treatment clinician prepares the patient for treatment by displacing clothing from the treatment area, which is the abdominal area from the bottom of the sternum to the iliac crest.
- The patient lies down on their back on the treatment table.
- The treatment clinician turns on the Ultimate Contour Mini device and sets it to the indicated parameters for this study: Time Setting of 30 minutes; Intensity Setting of 4.
- The treatment oil/fluid, a massage oil with a cottonseed or grapeseed oil base, is applied to the patient's skin over the area intended for exposure.

- The treatment clinician applies the treatment handpiece to the patient's skin in the intended treatment area.
- The treatment clinician presses the Activation button on the Ultimate Contour screen to begin energy emissions from the handpiece.
- The treatment clinician begins moving the handpiece along the skin with slight pressure to the handpiece to maintain contact with the skin, moving in circular, orbital motions approximately twice the diameter of the handpiece diameter, and progressively advancing in a linear direction from one edge of the treatment zone to the other in an overall back-and-forth approach.
- The treatment clinician continues application of the handpiece until either the proscribed 30 minutes has expired, or the patient indicates to halt the treatment due to discomfort.
- Once energy emissions cease, the handpiece is removed from the skin, and the treatment oil is cleaned off from the skin.
- The patient replaces clothing and is moved back to the assessment room.

**Post-Treatment Assessment (approximately 15 minutes):**

- The Post-Treatment assessing investigator observes the treated area for any redness, edema, swelling, or other indications specifically called for in the Anticipated Effects treatment record. The patient is asked for any unexpected sensations, for example sensations of high heat or of a "pins and needles" tingling effect in the tissue. These anticipated effects are documented in the treatment session record. Un-anticipated effects are recorded in the Adverse Event form.
- The patient is presented with the Stanford Pain Scale chart and asked to rate their overall pain and discomfort during the treatment. This is documented in the treatment session record.
- A waist circumference measurement of the abdominal region is made using the constant-tension tape measure. This measurement is recorded in the Post-Treatment Measurement record.
- The patient is provided with a study diary form, and instructed to document in the diary any unusual sensations, events, or bodily responses and to bring the form with them for the next visit.
- At the final treatment session only, the patient is provided with the Q-Post Survey to fill out.
- The patient is then scheduled for the next study session, and then excused.

**FOLLOW-UP (approximately 15 minutes):**

- The patient is scheduled for and arrives at the study site at the appropriate time points 1, 4, or 12 weeks after the final treatment.
- The date of the visit and the time of arrival will be documented Post-Assessment Measurement and Anticipated Effects forms.
- For the 1-week and 4-week visits, the patient fills out the WaistQ-Post Survey. For the 12-week follow-up, the WaistQ-12 Survey is filled out.
- The patient will have their waist circumference measured and documented by an investigator assigned to the post-treatment measurement and assessment activity, as described in the Measurement Tools and Methods section of this protocol. The patient will be asked for the study diary, and the investigator shall review the diary and discuss with the patient the items that are recorded about any abnormal body functions or observations that may be relevant to the treatment. If any are indicated, these will be documented in the patient record. The

investigator will also review observations and adverse events documented in previous sessions and discuss these with the patient. Additional record shall be made by the investigator as to whether past events and observations have been resolved or are still unresolved.

- For the 4-week or 12-week follow-up visits, the patient is provided with a study diary form, and instructed to document in the diary any unusual sensations, events, or bodily responses and to bring the form with them for the next visit. The patient is then scheduled for the 4-week or 12-week follow-up visits as appropriate.
- At the 12-week follow-up, additional review is made of the patient's Medical History and Medication forms and any new content for these forms is noted therein and discussed with the patient. If the 12-week follow-up visit is concluded and Adverse Event forms indicate any unresolved adverse results for the patient, additional follow-up is scheduled as appropriate until all adverse results are concluded.

#### DATA ANALYSIS AND FINAL REPORTS (approximately 2-3 weeks)

- Once all study participants have concluded the 12-week follow-up, unless participants are unable to be contacted or unwilling to participate in the follow-up, and all adverse interactions have a documented conclusion, analysis of the study data shall be conducted according to the Data Analysis section below.
- Data documented in the physical study records are populated into electronic spreadsheets.
- Data integrity is validated, and then data analysis is performed.
- Once data analysis is complete, final study reports shall be prepared, presenting the results of the study.

#### Monitoring

The study shall be monitored in the following manner:

- Training and Initial Inspection: The sponsor shall visit the study site and shall conduct an inspection of the site to determine that the site is adequate and appropriate for the activities described in this protocol. In particular, attention shall be given to ensuring that separation of treatment and the two assessment activities are accommodated to ensure patient and staff blinding is maintained, and that patient safety is ensured. Training shall be conducted for the investigators and staff regarding the study protocol, methods of measurement, and operation of the device.
- Informed Consent: The sponsor shall obtain copies of the signed informed consent forms prior to delivery of study devices.
- Surprise Inspection: At least twice during the course of study treatments, an independent third-party shall conduct a surprise inspection of the study site while treatments are being conducted, to review that the protocol is being followed, confirm that protection of human subjects is being employed, and ensure that treatment records are properly filled and maintained. Since the total duration of the device treatment period is anticipated to be only 4-6 weeks, the mandated 2 surprise visits are considered appropriate. If records or actions of investigation staff are found to be inconsistent, additional site inspections and possible additional training shall be employed.
- Collection of devices and records: Once all device treatments are completed, the sponsor shall retrieve the study devices and obtain copies of all treatment records. The sponsor shall review the patient records, and make especial note of adverse interactions contained in the records.
- Follow-up Records: At the conclusion of the follow-up visits, the sponsor shall collect the patient records from the follow-up visit. The sponsor shall compare and confirm that all adverse

interactions that have been documented have been resolved at this point. If any adverse interactions are still unresolved, the sponsor shall work with the investigator to continue follow-up with the affected patients to achieve resolution.

- Audit of the Records: An independent third-party shall perform a sampling review of the study records during the surprise visits, and shall conduct a full audit of all study records at the conclusion of the study. This audit shall include quality control verification of data uploaded to electronic format. The audit shall confirm that all indicated adverse effects, whether anticipated or not, have been followed through to conclusion and such conclusions are documented in the Case Record Forms.

### **Efficacy & Safety variables, including collection of adverse event data and anticipated adverse reactions**

#### **EFFICACY**

Input variables related to the determination of efficacy include the patient's age, gender, ethnicity, height, and weight (to determine the relative extent of obesity). Study output variables collected during this trial included the change in patient waist circumference as a primary indicator. Capture and collection of patient images may be useful for informational purposes, but are not a requirement of this study and shall not be used for any data analysis or study conclusions.

#### **SAFETY**

Input variables related to safety are reflected in the exclusion criteria. Primary among these is the effect the ultrasound treatment has on existing illnesses or conditions. There is concern that the delivered energy could adversely affect these conditions, making the patient's overall status worse. Other input variables for safety include the effect on localized tissue directly exposed to the ultrasound, as well as possible systemic effects that may occur.

Output data collected for safety include the patient's assessment of pain or discomfort experienced during or following the treatment, and questioning regarding any observations about systemic health that the patient may make during the overall trial. Any such comments or concerns from the patient are documented in the patient treatment records. Additionally, observations by the clinician about localized tissue response and patient general behavior were collected if any occurred and made part of the patient record.

#### **ADVERSE INTERACTIONS**

Anticipated adverse responses include:

- Localized inflammation, edema, and elevated temperature of the treatment area: Based on the proposed mechanism of action, the application of ultrasound and the disruption of cells could result in a localized increase in tissue temperature, accompanied by increased blood circulation through the insulted tissue.
- Localized pain or discomfort: The action of ultrasound of this frequency and intensity on nerve cells is not well understood. The same mechanism of action could trigger nervous cell responses interpreted by the brain as a pain response. The disruption and cavitation of adjacent adipose cells could also trigger a pain response.
- Possible system disruption: The applied ultrasound energy is intended to provide localized energy at the typical depth of tissue where sub-dermal adipose cells are found. The ultrasound energy could continue to propagate further into the body, reaching gastro-intestinal organs beneath the treated area. In generalized terms, there could be disruptions to digestive processes resulting from exposure to the ultrasound energy.

- Possible elevation of blood glucose levels: The disruption and lysis of adipose cells may release an increased amount of glycogen into the blood stream. Patients who present with diabetes or pre-diabetes or who are susceptible to variations in blood glucose levels may experience side-effects consistent with elevated glucose levels wherein they are unable to metabolize and/or process the glucose products adequately.
- Possible pigmentation changes of the skin: The action of ultrasound on the skin may alter the amount or chemical nature of pigments in the skin, causing discolorations relative to the surrounding skin.
- Possible aggravation of surgically compromised or wounded tissue: The action of ultrasound on tissue that has been disrupted, such as through surgical procedures, previous wounds, or previously or presently inflamed tissue, could create mechanical stresses on the wound boundaries and possible overcome connective tissues across the wound boundaries, resulting in re-opened or inflamed sites.
- Possible increased compromise of immuno-suppressed patients: Patients who are or have recently experienced systemic procedures or conditions that weaken or suppress the immune system may be further weakened as a result of this treatment, as the process is expected to utilize immune responses to clear away the treated sub-cutaneous tissues.

If any adverse events occur, such will be immediately reported to the principal investigator who will assess the events and make determinations about whether the study should be halted or modified, or whether the participant should be excluded from further participation in the study. The study sponsor shall also be notified of the adverse event and of the principal investigator's assessment and decision regarding any action towards the participant or the study.

## DATA ANALYSIS

### **Data quality assurance**

Patient and study data will be documented on physical, printed patient treatment session sheets. The completed sheets will be provided to the sponsor, who has the responsibility of uploading the data into electronic files for statistical analysis and processing. Calculations made from the data will be conducted in the electronic files, and the accuracy of calculations provided by the electronic spreadsheets shall be relied on. The clinicians and those who participate in the data collection will not have access to the electronic files, calculations, or analyses. Electronic data management tools are also employed to perform the statistical analysis of the key data.

Accuracy of the measurements made by the tape measure are verified by the sponsor. This is confirming the calibration status of the device via the manufacturer's certificate of calibration, as well as verification by measuring rigid metal cylinders with the device and comparing the measurements with NIST traceable calibrated calipers to measure the sample diameter from which the circumference can be calculated.

Where patients discontinue participation in the study, or key data is not documented properly on the treatment sheets, data from such patients shall not be incorporated in the statistical analysis of the data.

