## **Inclusion/Exclusion Criteria**

Inclusion in the study consists of the following criteria:

- Age equal to or above 18.
- Body Mass Index  $\geq 25$ .

Exclusion from the study consists of the following criteria:

- Age equal to or below 17.
- Body Mass Index  $< 25$ .
- Open sores, wounds, or otherwise compromised skin in the treatment area
- History of keloid formation, hypertrophic scarring, or abnormal/delayed wound healing.
- Known or suspected pregnancy, or active nursing.
- General systemic conditions of arteriosclerosis, anemia, aortic aneurysm, or hypertension.
- Liver conditions such as hyperlipidemia, hepatitis, liver disease, or abnormal liver function
- Diabetes or blood-glucose sensitivity
- Any prior invasive cosmetic surgery to the waist or abdominal area, such as liposuction.
- Hernias or diastasis recti within the treatment area.
- Concurrent, or within the last 6 months, participation in any clinical trial for another device or drug.
- Existing bacterial or viral infections (influenza, rhinovirus, hepatitis, pneumonia, tuberculosis, and the like)
- Presence of acne vulgaris, herpes zoster, psoriasis vulgaris, or similar skin conditions in the treatment area.
- Any type of cosmetic treatment to the target area within the last 6 months.
- Implanted active medical device anywhere in the subject, or metallic or polymeric implants in the vicinity of the treatment area.
- Currently undergoing, or recently underwent, chemotherapy or radiation treatment.
- Per the investigator's discretion, any physical or mental condition which may compromise the patient's safety or welfare.
- Failure to complete the study as outlined.

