## **Statistical Methods**

Single factor ANOVA analysis will be used to determine if the extent of circumference reduction in the test group is statistically significant over changes in the control group. Additional correlation assessment will be performed to identify any potential relationships between patient data sets, and single-factor ANOVA assessment applied to those correlations as applicable. Missing or incomplete data shall be populated using least-favorable data from participants who did complete the study.

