The device in question, presently branded as the Ultimate Contour Mini, is at the stage of development where functional demonstration devices have been constructed and assembled. The design at present is representative of the final released configuration to the extent that third-party safety testing and certification has been conducted on the device and the device demonstrated to be safe relative to the design and constructional requirements of IEC 60601-1 (3rd Edition) for safety of electrical and electronic medical devices and systems, as well as IEC 60601-1-2 (3rd Edition) for electromagnetic compliance safety and performance of electrical and electronic medical devices and systems.

The study has a fixed endpoint of three (3) treatment sessions and three follow-up visits per patient, to the extent that a sufficient quantity of patients have completed the study. Given that a gap of 6-8 days will exist between treatments, the scheduling of patients will be staggered as necessary to best utilize investigator and equipment resources, with the overall course of the study treatments is not expected to exceed 6 weeks of total study time. The follow-up visits are mandated to occur at intervals of one, four, and twelve (12) weeks from the date of final treatment. Once all patient treatments are completed, analysis of the data shall be performed by the sponsor (and reviewed by an independent statistical resource) to determine the extent of success in achieving the primary and secondary objectives.

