### **Sequence and duration of study period**

Patients will be scheduled according to each one's availability for the first of three treatment sessions. After each particular treatment, the patient will be scheduled for the next visit, with it being preferred that subsequent treatments occurring between 6-8 days into the future of the present treatment. Each patient is to receive 3 treatment sessions, with each session featuring the same device settings and conditions of application relative to which study group the patient is assigned to. Overall, the study treatments are anticipated to take about 6 weeks to accomplish. The patient is recalled 1 week, 4 weeks, and 12 weeks after the last treatment for follow-up evaluation.

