### **Statistical methods planned, including handling data exclusion, analysis of sub-groups if any**

Any patient that did not conclude all three treatments shall be excluded from the analysis. If there are fewer than 37 patients remaining after the study concludes and exclusions are applied, than no analysis shall take place and additional study subject enrolled until a minimum of 40 completed participants exist. In the event that a patient concludes at least one treatment session, but afterwards discontinues

participation in the study, the presence of the patient in the study shall be acknowledged for data analysis purposes. Missing data for such acknowledged participants shall be fulfilled by inserting the least favorable result obtained realized from among all test subjects who did complete the study. Statistical analysis shall then proceed on the fully populated study data.

Primary analysis shall consist of applying the Anova single-factor acceptance test evaluating the change in waist circumference based on the data collected by the tape measure. A confidence of  $P=0.05$  shall be applied. The results of this data shall be directly applied to determining if the primary objective of the study has been met.

A correlation analysis shall be applied to all variable data recorded, as well as key calculations from the data, to identify any potential two-way connections or relationships between sets of data. Any correlations scoring a magnitude of 0.85 or greater shall be discussed and if appropriate, Anova single-factor analysis applied to determine if there is statistical significance to the relationship and any statements that might be supported by the data. Of primary interest is any impact the starting BMI might have on the amount of change, and any impact that gender may impart to the outcome.

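### The plan drops a patient whole when undefined 'key data' are poorly documented, with no exception for a completer with valid waist values, and the synopsis gives a conflicting rule

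*Combined protocol and SAP*

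**What the plan says.** The combined protocol and SAP handles incomplete or badly recorded data in several places.

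- **Data quality assurance.** After naming patients who discontinue, the sentence continues: "or key data is not documented properly on the treatment sheets, data from such patients shall not be incorporated in the statistical analysis". The two conditions are joined by 'or', so the second also reaches patients who finish. What is removed is the patient's data, not the faulty item.
- **Synopsis, Statistical Methods.** "Missing or incomplete data shall be populated using least-favorable data from participants who did complete the study". Here an incomplete record is filled and the patient stays.
- **Statistical methods planned.** "Any patient that did not conclude all three treatments shall be excluded from the analysis". For patients who had at least one session and then stopped: "Missing data for such acknowledged participants shall be fulfilled by inserting the least favorable result obtained realized from among all test subjects". Poor documentation is not mentioned as a ground for exclusion.
- **Eligibility lists (synopsis and main text).** The last exclusion item is "Failure to complete the study as outlined".
- **Treatment interval.** The Introduction says "Given that a gap of 6-8 days will exist between treatments", and the synopsis Methodology likewise states the gap as fixed. Sequence and duration of study period says "with it being preferred that subsequent treatments occurring between 6-8 days into the future of the present treatment".

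On who applies the rule: under Monitoring the sponsor collects and reviews the patient records, noting adverse interactions in particular. Under Data quality assurance it is the sponsor "who has the responsibility of uploading the data into electronic files for statistical analysis and processing". The Introduction has the sponsor perform the analysis, with independent statistical review.

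**The concern.** A valid primary endpoint could be lost because another entry on a treatment sheet is defective. Neither the data that count as key nor the standard of proper documentation is stated, so the decision is a matter of judgement. The party making it has the waist results and safety records in hand. The plan describes no exclusion list fixed before outcomes are seen and no blinded data review.

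The conflict with the synopsis widens that judgement. Deleting a record and scoring it worst-case push the mean in different directions, and the text supports either.

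At stake are the 1-inch threshold at week 12 and possibly the safety verdict. The Study Objectives set the safety conditions as zero-event rules (for example, no patient with a pain rating of 4 or more), so one record can decide them.

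**Working it through.** **The plan's own figure.** From Sample size: n = 2 × (1.96 + 0.84)² × 1.50² / 1.0² = 2 × 7.84 × 2.25 = 35.28, which rounds up to 36. The t-based version gives 36.3, so 37, which is the stated figure. The SD of 1.50 inches and the typical response of 0.75 inch used below come from the same section.

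**Assumptions not in the documents.** There are 44 completers; 10% or 20% have a documentation defect; changes are normal with SD 1.5; the 1-inch criterion is read as a group mean; true losses are 0.75 inch (the cited typical response) and 0.9 inch (near the cutoff).

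**Step 1: even-handed removal.** If defects are unrelated to outcome and all flagged patients are dropped, the expected mean does not move. The loss is 4.4 to 8.8 patients (10% or 20% of 44). The floor for analysis is 37, so 7 of 44 can go. The binomial chance of 8 or more defects in 44 is about 7% at a 10% rate and 68% at 20%. Below the floor, the plan reopens enrolment.

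**Step 2: one-sided removal.** Suppose a fraction f is flagged and only flagged patients below the mean are dropped. The below-mean half averages 1.5 × √(2/π) = 1.197 inches under the mean, so

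shift = 0.5 × f × 1.197 / (1 − f/2).

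- f = 0.10: 0.0598 / 0.95 = 0.063 inch
- f = 0.20: 0.1197 / 0.90 = 0.133 inch

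Simulation of 44 patients gives 0.062 and 0.132. As a ceiling, dropping the 4 lowest of 44 gives about 0.26 inch.

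**Step 3: effect on the 1-inch threshold.** With about 40 patients left, SE = 1.5/√40 = 0.237. The chance of an observed mean of at least 1 inch is 1 − Φ((1 − true loss − shift)/0.237).

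| True loss | No shift | +0.06 | +0.13 |
|---|---|---|---|
| 0.75 inch | 15% | 21% | 31% |
| 0.9 inch | 34% | 43% | 55% |

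For a single group tested against zero, significance adds no further hurdle: a mean of 1 inch is 1/0.237 = 4.2 standard errors. The documents disagree on whether there is a control group. With one, these figures describe the test-group mean only.

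**Step 4: safety, if the same removal applied.** Take an assumed 2% per-patient risk of a disqualifying pain score and 50 patients. The chance of no event is 0.98⁵⁰ = 36%. If one affected patient could be left out, it is 0.98⁵⁰ + 50 × 0.02 × 0.98⁴⁹ = 74%. At 1% the pair is 61% and 91%; at 5% it is 8% and 28%. This is an upper bound, conditional on an inference discussed below.

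**The case against.** **Safeguards exist.** Data integrity is validated before analysis (Data analysis and final reports). At least two surprise third-party inspections check that records are properly filled, and an independent party audits all records and the uploaded data (Monitoring). Independent review of data handling is planned (Introduction, Sample size). A reader might infer that the sponsor is free to discard results it dislikes; the documents do not support that. What remains is that none of these checks has a stated exclusion standard to test a removal against.

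**The trigger may be narrow.** The rule concerns key data, not any clerical slip, and waist change is the primary indicator. If key data means only the waist values, the patients removed have no usable change score anyway. That is a fair reading, but the text does not settle it.

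**'As outlined' as a rule against completers.** A reader might infer that a late session removes a patient who finished. The eligibility line speaks of failing to complete, and no analysis rule links timing to removal. A missed or late session is also known on the day, well before the week-12 waist. The line is misplaced, since it cannot be assessed at enrolment, and could be read as a post-hoc exclusion. That is all the text supports.

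**Safety data lost.** This too is an inference. The rule governs the statistical analysis, while adverse effects are still recorded, followed and audited to conclusion. But no safety population is defined, so nothing keeps a removed patient in the zero-event conditions.

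**The size is a scenario.** The defect rate and number of completers are assumed, and the shift requires one-sided enforcement. This stands, and is why a range and the zero-shift case are shown.

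**Conclusion.** The point holds as a defect in the exclusion rule. The plan states whole-patient deletion on an undefined documentation standard, does not protect a completer with valid baseline and week-12 waists, and contradicts its own synopsis on incomplete data. Even-handed use would cost precision only. Selective use, under the stated assumptions, would raise the mean by about 0.06-0.13 inch. The chance of reaching 1 inch would then rise by some 6 to 16 percentage points at a true loss of 0.75 inch (15% to 21-31%) and by 9 to 21 points at 0.9 inch (34% to 43-55%). These figures show what the wording permits; they do not predict conduct. The exposure of the safety conditions is an inference from the missing safety population. Severity: should be fixed before enrolment.

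**What to change.** 1. In Data quality assurance, replace the documentation clause with: *Documentation defects are queried against source before the data are locked and analysed. An item that stays unusable is treated as missing for that item only. All other data of that patient stay in the analysis. Every patient with a baseline and a week-12 waist is in the primary analysis, and every treated patient is counted in the safety conditions of the Study Objectives.*
2. For an unusable baseline or week-12 waist, apply one missing-data rule, stated identically in the synopsis Statistical Methods, Data quality assurance and Statistical methods planned.
3. Remove the item on failing to complete as outlined from both eligibility lists. State that a timing deviation is recorded and does not by itself remove a patient from the analysis.
4. Reconcile the synopsis Methodology, the Introduction and Sequence and duration of study period on whether the 6-8 day gap is required or preferred.

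The cost is wording in several sections and some site queries before lock. The planned sample size does not change.
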